1 STUDY SUMMARY

1.1 Synopsis

Title:	GEnetic counseling Through VIRTUAL visits in Parkinson's Disease
Short Title:	GET Virtual PD
Study Description:	This research tests novel approaches to pre-test counseling and post-test disclosure of genetic information in people with PD. Participants will be randomized to receive different methods of genetic counseling in a factorial design. In both pre- and post-test counseling phases, novel genetic counseling methods will be compared to telephone genetic counseling to demonstrate equivalence. The primary outcomes will be equivalence on genetics knowledge and outcomes scales, and the revised impact of events scale. The purpose is to develop effective and scalable approaches to genetic counseling. This work is crucial for patient safety and will improve access to care through novel genetic counseling approaches.
Objectives:	The primary objectives of this study are to determine the efficacy of (1) an audiovisual, web-based genetic counseling tool called the Interactive, Multimedia Approach to Genetic counseling to INform and Educate in Parkinson's Disease (IMAGINE-PD), and (2) disclosure of genetic testing results through a real-time, videoconference telegenetics platform compared to telephone counseling.
Primary Endpoints:	Genetics Knowledge Scale 4 weeks after pre-testing counseling, Revised Impact of Events Scale 3 months after genetic results disclosure, Genetic Counseling Satisfaction Scale (GCSS) immediately after disclosure counseling.
Secondary Endpoints:	GCOS, GDS, STAI, PDQ-39, C-SSRS, MoCA
Study Population:	N= 320 (80/counseling group) Parkinson's disease patients seen at the University of Pennsylvania Parkinson's Disease and Movement Disorders Center (PDMDC) who are also enrolled in the PDMDC Genetics Biobanking Protocol (IRB 830237), aged 21 and over.
Phase:	NA

Description of Sites/Facilities	Single-site
Enrolling Participants:	UPENN PDMDC
Description of Study Intervention:	For pre-test counseling, an audiovisual, web-based genetic counseling tool called the Interactive, Multimedia Approach to Genetic counseling to INform and Educate in Parkinson's Disease (IMAGINE-PD) will be compared to telephone counseling. Content, layout, and user testing for IMAGINE-PD were developed using the NIH guideline for usability and user testing. Expert input was obtained from movement disorders and neurogenetics specialists. For post-genetic test results disclosure web- based video conference genetic counseling will be compared to telephone genetic counseling.
Study Duration:	36 months

Participant6 monthsDuration:

[figure not shown]

1.3 Schema

Study Schema: Overall Design.

Schedule of Events:

aute of Events.		
e -30-0 days S	Screening (Total n=385)	
• Screen potential participants by inclusion and exclusion criteria, call to invite to participate		
MoCA		
r 0 (Visit 1)	Randomization (N=80/group)	
IMAGINE-PD/Virtual, IMAGINE-PD/Telephone, Virtual/Virtual, Virtual/Telephone		
r 0 (Visit 1)	Baseline assessments/ Study Intervention	
Obtain informed consent, register in REDCap, train on BlueJeans platform, assign GUID		
• Pre-Counseling: Demographics, med history, medications, family history, GKS, GDS, STAI, PDQ-39		
Administer pre-test genetic counseling via IMAGINE-PD or virtual visit		
Observe saliva collection for genetic confirmation testing		
Post-Counseling: GCSS		
28-56 (Visit 2)	Genetics disclosure visit	
Pre-disclosure: GKS (primary outcome)		
Administer Post-test Genetic Counseling via virtual visit or telephone		
Post-disclosure: GCSS (primary outcome)		
Day 90-118 (Visit 3)Genetics disclosure follow up (3 months post-disclosure)		
28-56 (Visit 2) 0 Pre-disclosure: GKS (primary outcomession) 0 Administer Post-test Genetic Counce 0 Post-disclosure: GCSS (primary outcomession) 0	rome) seling via virtual visit or telephone utcome)	

Protocol 843748-
GET VIRTUAL PD
IMAGINE-PD

• IES-R, (Primary outcome), GCOS, GDS, STAI, PDQ-39, C-SSRS	
Day 210-238 (Visit 4)	End of study assessment (6 months post-disclosure)

• IES-R, GCOS, GDS, STAI, PDQ-39, C-SSRS

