3 STUDY OBJECTIVES AND ENDPOINTS

Outcomes to be studied include cognitive and affective outcomes, which will be measured via questionnaire-based scales (See **Table 2**). The questionnaires will be administrated electronically utilizing REDCap, a secure online data collection tool. Outcome measures will be collected at multiple time points throughout the study; however, the primary outcomes include Genetics Knowledge Scale at 4 weeks after pre-testing counseling, Genetics Counseling Satisfaction Scale immediately after disclosure counseling, and the Revised Impact of Events Scale 3 months after genetic results disclosure. A data monitoring plan will be in place to ensure patient safety.

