4 STUDY PLAN

4.1 Study Design

The proposed study is a single-center, prospective, factorial, non-inferiority, randomized cohort design to test the equivalence of telephone genetic counseling model to novel forms of pre-test genetic counseling and telegenetic results disclosure in participants with PD carrying a *GBA* or *LRRK2* variant (PD+*gene*+), participants with PD not carrying a *GBA* or *LRRK2* variant (PD+*gene*+), participants with PD not carrying a *GBA* or *LRRK2* variant (PD+*gene*-), and a group of at-risk *LRRK2* or *GBA* variant carriers without PD (PD-*gene*+). Participants will be recruited from a single center at the University of Pennsylvania Parkinson's Disease and Movement Disorders Center. A separate biobanking protocol, called the Molecular Inegration in Neurological Diagnosis MIND Cohort (UPenn IRB # 830237) enrolls subjects with PD and collects optional consent for recontact based on eligibility for additional studies. Subjects would be recruited to GET Virtual PD after enrolling MIND and after a blood or saliva sample has been collected and research-based genetic testing has been performed, but before clinical-confirmation genetic testing. GET Virtual PD will serve as the follow study to MIND that will allow access to genetic counseling and clinical genetic confirmation testing.

Enrolled participants will be randomized into one of 4 groups based on pre- and postgenetic test counseling: (1)IMAGINE-PD/Virtual, (2)IMAGINE-PD/Telephone, (3)Virtual/Virtual, and (4)Virtual/Telephone, stratified by genetic group. They will receive pretest genetic counseling through the Interactive Multimedia Approach to Genetic counseling to INform and Educate in Parkinson's Disease (IMAGINE-PD) website or via virtual visit with a genetic counselor. Participants will be asked to complete questionnaires on genetic knowledge, cognitive and affective outcomes prior to and 4 weeks after pre-test genetic counseling. All participants will then have clinical genetics results disclosure via virtual visit or by telephone with a genetic counselor. Patient-reported cognitive and affective outcomes will be measured 6 weeks and 6 months after genetic results disclosure. The hypothesis is that performance on the genetic knowledge scale and the revised impact of events scale will be equivalent between counseling groups at 4 weeks after pretest counseling and 6 weeks post disclosure, respectively.

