12 APPENDIX

12.1 Schedule of Activities (SoA)

Procedures	Screening Day -30 to 0	Study Visit 1, Day 0	Study Visit 2 Day 28-56	Study Visit 3 Day 90-118	Study Visit 4 Day 210-238
Informed consent		Х			
Demographics		Х			
Medical History ^a		Х			
MoCA	Х				
Randomization		Х			
Pretest Counseling (Virtual or IMAGINE-PD)		Х			
Genetic Testing		X ^d			
Genetic Test Disclosure (Virtual or Telephone)			Х		
Genetics Knowledge Scale		X ^b	X ^b		Х
Geriatric Depression Scale		Х		Х	Х
State Trait Anxiety Scale		Х		Х	Х
Parkinson's Disease Questionnaire-39		Х		Х	Х
Genetic Counseling Satisfaction Scale		Xc	Xc		
Revised Impact of Events				Х	Х
Columbia Suicidality Rating Scale				Х	Х
Genetic Counseling Outcomes Scale				Х	Х
Complete Case Report Forms (CRFs)	Х	Х	Х	Х	Х
Adverse Events Review		Х	Х	Х	Х

^aMedical History includes medical history, medication review, family history review. ^bPrior to genetic counseling. ^cAfter genetic counseling. ^dFulgent or in-house testing for confirmation tests.

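### The primary IES-R is set at 3 months after disclosure in most sections and at 6 weeks in section 4.1, while the visit grid allows only 34 to 90 days

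*Combined protocol and SAP*

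**What the plan says.** **Three months.** The synopsis (1.1) lists the primary endpoint as "Revised Impact of Events Scale 3 months after genetic results disclosure". Section 3 repeats it, and sections 9.1 and 9.4.2 carry the same 3-month time into the hypotheses and the primary analysis. Section 1.3 marks the IES-R as a primary outcome at the visit headed "Day 90-118 (Visit 3)Genetics disclosure follow up (3 months post-disclosure").

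**Six weeks.** Section 4.1 says: "Patient-reported cognitive and affective outcomes will be measured 6 weeks and 6 months after genetic results disclosure". The hypothesis at the end of that section also puts the IES-R comparison at 6 weeks after disclosure.

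**The visit grid.** Section 12.1 sets Visit 1 at Day 0. Disclosure is at "Study Visit 2 Day 28-56", the primary IES-R at "Study Visit 3 Day 90-118" and the last IES-R at "Study Visit 4 Day 210-238". Section 1.3 uses the same days and labels the last visit "End of study assessment (6 months post-disclosure").

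No passage says that Visit 3 is counted from the actual disclosure date, and none gives a tolerance around 3 months.

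**The concern.** The IES-R difference is the quantity from which section 9.2 derives the sample size, and section 9.4.2 names it as the primary endpoint. Section 8.1 says the scale covers the past 7 days, so the time since disclosure decides which week of a participant's experience is measured. If the label says 3 months and the calendar delivers about 2, the report will describe a time point at which most of the data may not have been collected.

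There is an operational problem too. Staff who book Visit 3 at 90 days after disclosure will usually fall outside the printed window, and section 10.1.9 treats any departure from the protocol as a deviation. Staff who keep to the window will usually see the participant before 90 days. Section 9.3 also gives completion of the 3-month visit as its example of per-protocol compliance, so the ambiguity reaches an analysis population. The interval at which a visit was held cannot be corrected afterwards.

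**Working it through.** **Inputs** (sections 1.3 and 12.1): disclosure, Visit 2, Day 28 to 56; primary IES-R, Visit 3, Day 90 to 118; last IES-R, Visit 4, Day 210 to 238. Day 0 is Visit 1. Months are converted at 30.44 days.

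**Step 1. Does the grid reproduce the 3-month label?** Gap = Visit 3 day minus Visit 2 day.
- Shortest: 90 − 56 = 34 days.
- Longest: 118 − 28 = 90 days.
- Same point in both windows: 90 − 28 = 118 − 56 = 62 days, about 2.0 months.
- Spread between in-window participants: 90 − 34 = 56 days.

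It does not, except at one extreme.

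**Step 2. Gap allowed for a given disclosure day d.** The range is 90 − d to 118 − d.

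| Disclosure day | Allowed gap (days) |
|---|---|
| 28 | 62-90 |
| 42 | 48-76 |
| 56 | 34-62 |

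Each window holds 29 days, so there are 29 × 29 = 841 day pairs:
- 90 days or more: one pair, Day 28 with Day 118.
- 84 days (12 weeks) or more: only for disclosure on Day 28-34.
- Exactly 42 days (6 weeks): only for disclosure on Day 48-56.

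These counts show what is possible. They are not forecasts, because the documents do not say how visits fall within their windows.

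**Step 3. Where each stated time would put Visit 3.**
- 90 days after disclosure: 28 + 90 to 56 + 90 = Day 118-146. For disclosure on Day 29-56 it is Day 119-146, entirely outside the printed window.
- 42 days after disclosure: 28 + 42 to 56 + 42 = Day 70-98.

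Neither is Day 90-118.

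**Step 4. The same check on Visit 4.** Gap from disclosure: 210 − 56 = 154 to 238 − 28 = 210 days. At matched points it is 210 − 28 = 182 days, or 6.0 months, which agrees with its label.

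**Step 5. Would another anchor help?** Suppose the printed days are counted from disclosure. Visit 3 is then at 90-118 days (3.0-3.9 months), which fits, but Visit 4 is at 210-238 days (6.9-7.8 months), which does not fit 6 months. Under either anchor, Visits 3 and 4 are 210 − 90 = 238 − 118 = 120 days apart at matched points. Labels of 3 and 6 months imply about 3 × 30.44 = 91 days. No single anchor makes both labels true.

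**The case against.** The best defence is that this is a labelling fault. All four arms follow one schedule under 1:1:1:1 randomisation, so the IES-R contrast is a fair comparison whether Visit 3 falls nearer 2 or 3 months. The sample size does not depend on the time point, and the other two primary outcomes are untouched. All of that stands. It leaves open what the endpoint describes and which visits count as on time.

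Second, the wide windows suggest that exact days were never meant. With an assumed tolerance of 14 days (gap of at least 76), Visit 3 can be in window for disclosure on Day 28-42. With 28 days (gap of at least 62), it can be for every disclosure day, since 118 − 56 = 62. The arithmetic is right, but no such tolerance is written, and the second would call 62 days three months.

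Third, the statements are not wholly disjoint, and 3 months is plainly the majority. The 34-90 day range contains 42 and touches 90, and the 6-week wording appears only in section 4.1, so it may be leftover. Even without it, the grid conflicts with the 3-month label.

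Fourth, counting from disclosure puts Visit 3 on time. It then breaks the Visit 4 label and departs from the single Day 0 scale of section 12.1.

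Fifth, section 7.3 allows rescheduling within 8 weeks. That concerns missed visits and does not set a target time.

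Finally, nothing in the documents shows that IES-R scores differ between 62 and 90 days. That is so, and no size of effect on the scores is claimed here.

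**Conclusion.** The concern holds. The current text gives 3 months, 6 weeks and a calendar that defines neither. Taken as printed and counted from Day 0, the primary IES-R falls 34-90 days after disclosure, and at 62 days for everyone if Visit 3 tracks Visit 2 within its window. Taking 3 months as 90 days, the label and the window cannot both be met for anyone disclosed after Day 28.

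The size of the problem is a shortfall of 90 − 62 = 28 days at matched window points and a possible spread of 56 days between participants. No percentage of participants affected can be given. The documents do not say how the mismatch arose or which time is intended. It should be settled because it concerns the definition of the endpoint on which the trial is sized, and because the printed schedule would generally yield a result at about two months reported as three.

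**What to change.** State one time for the primary IES-R and bring sections 1.1, 1.3, 3, 4.1, 9.1, 9.4.2 and 12.1 into line with it. This can be done by moving the Visit 3 window or by renaming the endpoint to match the window. Which time is intended is for the sponsor to decide. Check that the per-protocol example in section 9.3 still names the right visit.

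Define the Visit 3 and Visit 4 windows as days from the actual disclosure date, and state that anchor in a footnote to the 12.1 table. Record days since disclosure with each IES-R, so that the realised timing can be reported. In the same edit, check the 6-month participant duration in section 1.1 against the last visit: Day 210-238 is 6.9-7.8 months after Day 0.

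The cost is amendment wording, plus a REDCap window change if Visit 3 moves. There is a trade-off. Moving Visit 3 also moves the first scheduled C-SSRS, GDS and STAI after disclosure (12.1), which the sponsor must weigh. Renaming the endpoint leaves those assessments in place but gives up the stated 3-month endpoint.

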2 INTRODUCTION AND RATIONALE

2.1 Study Rationale

The search for a disease-modifying therapy for Parkinson's disease (PD) remains ongoing despite decades of basic research and unsuccessful clinical trials. Novel treatments targeting carriers of pathogenic variants in the glucocerebrosidase (GBA) and LRRK2 genes, the strongest genetic risk factors for PD, show great promise. The frequency of GBA and LRRK2 variants is low in the general PD population (5-10%, and 1-2%, respectively), and therefore identifying eligible patients is a challenge. To achieve this goal, broad genetic testing will become the norm, departing from current practice. Broad genetic testing will capture research-eligible patients and in the future will identify populations of genetic variant carriers for precision-medicine approaches. However, such an expansion in genetic testing raises concerns about the capacity to expand genetic counseling, an essential component of clinical-genetic medical care. The current standard-of-care model, which utilizes a two-visit, face-to-face counseling model, is limited by access to trained genetic counselors to provide pre- and post-genetic testing counseling. Alongside such an expansion in genetic testing, it is essential that we develop novel models for safe and effective communication of genetic information at scale. Alternative genetic counseling and disclosure models involving video or web-based tools are currently being developed or are already in use. However, no studies have examined these approaches in the PD population.

The goals of this research study are to determine the efficacy of (1) an audiovisual, web-based genetic counseling method called the Interactive, Multimedia Approach to Genetic counseling to INform and Educate in Parkinson's Disease (IMAGINE-PD), and (2) disclosure of genetic testing results through a real-time, videoconference telegenetics platform.

2.2 Background

Clinical Genetics of Parkinson's disease

PD was thought to be a sporadic disorder until the late 1990s when genetic mutations responsible for the disease were identified in the synuclein gene (*SNCA*).¹ Since that time significant progress has been made in understanding the genetics of PD. A number of rare mutations have been identified in the genes *Parkin*, *DJ-1*, *Pink1* and *SNCA*, which are highly penetrant causes of PD.^{1–4} Additionally, variants with incomplete penetrance have been shown to increase risk of PD in certain populations, including in the gene encoding glucocerebrosidase (*GBA*),⁵ the strongest genetic risk factor for PD. It is estimated that PD is 27% heritable based on genetic variants in genome-wide association studies.⁶

Genetic testing is rarely pursued in the clinic because genetics do not currently play a role in the diagnosis or treatment of patients with PD. However, knowing one's genetic status is already of key importance for clinical research purposes, as therapies targeting carriers of *GBA* variants are being studied in Phase I and II clinical trials. Evidence in PD has demonstrated that patients

Page 14 of 41

are interested in learning about their genetic data.^{7,8} Moreover, at the University of Pennsylvania (UPenn), my Mentor [name] and I have launched an initiative to approach all PD patients seen in our Parkinson's Disease and Movement Disorders Center (PDMDC) for research consent. The first consecutive 376 PD patients approached through this Molecular Integration in Neurological Diagnosis (MIND) Initiative were surveyed about their interest in participating in genetics research with the potential to learn their own results. Strikingly, 98% indicated interest in participating, as well as interest in knowing their genetic results. It is unknown how many will agree to perform clinical confirmation testing. Expanded access to genetic testing is also occurring on a national level in an effort supported by the Parkinson Foundation called PD Generation, which provides genetic counseling and genetic testing to patients with PD. UPenn is a pilot site for this clinical trial and I am the site investigator. Although interest is high, practical limitations exist with an expansion in genetic testing and counseling in PD.

Novel Genetic Counseling Approaches are Needed in PD

The current genetic counseling model relies on a two-visit, face-to-face, pre-test counseling and post-test disclosure model to ensure informed consent, understanding, healthy psychosocial response, and preventive behaviors.⁹ There are many practical limitations to this approach including lack of access to trained genetic counselors, travel and cost restrictions, and the inability to provide effective counseling in the absence of a trained counselor. To address these challenges in other diseases, alternative approaches to genetic counseling have been developed for both pre-and post-test counseling methods by co-Mentor [name]. In the domain of pre-test counseling, for instance, the Alzheimer's Prevention Initiative Generation studies utilized video-based pre-test genetic counseling to convey information on *APOE* in Alzheimer's disease risk.¹⁰ Pre-test counseling via a web-based, interactive tool has also been utilized in the Returning Genetic Research Panel Results for Breast Cancer Susceptibility (RESPECT) Study (R01 CA190871: [name]).¹¹

Table 1. Change in patient reported outcomes after pre-disclosure and post-disclosure visits by eHealth pre-disclosure			
delivery as compared to traditional genetic counseling ¹¹			
Outcome	Change from BL to post-V1	Change from BL to post-V2	
Knowledge	NSS	NSS	
HADS anxiety	-1.0; p=0.03	NSS	
HADS depression	NSS	-1.1, p=0.002	
IES cancer worry	NSS	NSS	
Uncertainty	-1.4, p=0.04	NSS	
N=216-246, BL = baseline, V1 = pre-disclosure counseling or eHealth alternative (participant choice); V2 = phone disclosure with a genetic counselor (GC), NSS = no statistically significant difference from those who received pre-test counseling with a GC; all p values adjusted for baseline differences between non- randomized groups			

Data from **RESPECT** studies suggest that web-based alternative delivery methods of pre- and post-test genetic counseling cancer are acceptable to many patients and are associated with similar outcomes to traditional pre-test counseling with a genetic provider. To date, 211 (81%) have chosen pre-disclosure education by web-based method. Change in knowledge, anxiety, cancer-specific distress and uncertainty did not differ from baseline to post-disclosure between pre-disclosure education approaches. Further, the web-based

approach was not associated with any significant increase in distress or decline in knowledge after receipt of result as compared to those who chose pre-disclosure genetic counselor education (See

Protocol 843748-
GET VIRTUAL PD
IMAGINE-PD

Table 1).¹¹ The risks and benefits of alternative forms of pre- and post-test genetic counseling in PD has not been evaluated. As our knowledge of the genetics of PD expands, so too does our need for scalable approaches to counseling that are effective and safe.

2.3 Risk/Benefit Assessment

2.3.1 Known Potential Risks

This study provides genetic counseling and testing to all participants. The method of genetic counseling varies between randomization groups. There are no known risks that differ between forms of genetic counseling including web-based, telephone, or virtual visit methods. Potential risks of genetic counseling include anxiety, stress, or discomfort that can arise during genetic counseling. Genetic counseling during this study will be conducted by trained genetic counselors following clinical guidelines genetic counseling in PD. For participants randomized to IMAGINE-PD, participants will have access to a genetic counselor via email for any follow up or clarification questions. The risks of genetic testing are relevant to all participants, which include the potential for emotional, social, or financial consequences of the testing results. Some people may feel angry, sad, anxious, or guilty about the results. There is also a risk of genetic discrimination or of re-identification of deidentified genetic results.

